#### Vaccine reactogenicity

Counts and percentages of solicited local and systemic reaction frequency and severity among study cohorts (various CD4 counts and ages) will be summarized.

Adverse events will be classified by Medical Dictionary for Regulatory Activities (MedDRA®) system organ class and preferred term, severity, seriousness, investigator causality assessment, and time since vaccination.

Safety listings will display all safety events, including a separate display of solicited post-treatment reactions, and all other AEs.

#### Vital signs & clinical laboratory measures

Mean values for each measure, including  $\pm$  one standard deviation, will be summarized for each treatment group. Shift tables may also be generated if a significant frequency of abnormalities is noted. Extreme values will be discussed individually.

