#### 3.2 Secondary Objective(s)

- (1) **Objective:** Evaluate VSV viremia and shedding after administration of V920.
- (2) **Objective:** Evaluate ZEBOV-specific antibody responses induced by V920 through D180 and D365.
- (3) **Objective:** Evaluate the impact of V920 on HIV viral load, CD4 counts, and CD4/CD8 ratio.
- (4) **Objective:** Evaluate the safety and tolerability of two doses of V920 in HIV-infected adults and adolescents administered 56 days apart.
- (5) **Objective:** Evaluate the immunogenicity of two doses of V920 administered 56 days apart via ZEBOV-specific antibody responses induced by V920 at D28 post-dose 2 in HIV-infected adults and adolescents.

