#### 4.2.3.2 Safety Endpoints

1. Primary endpoints:
  - a. The occurrence of adverse events, in all participants, in all cohorts:
    - i. The occurrence of each solicited local and systemic AE, during a 14-day follow-up period following each vaccination, and fever, arthritis, arthralgia, rash and blisters/vesicular lesions during a 42-day follow-up period following vaccination.
    - ii. The occurrence of any hematological (hemoglobin level, WBC, lymphocyte, neutrophil, eosinophil and platelet count) and biochemical (ALT, AST and creatinine) laboratory abnormality at days 0, 3, 7, 14, and 28 after each vaccination.
    - iii. The occurrence of any unsolicited AE, during a 42-day follow-up period after each vaccination.
  - b. The occurrence of vaccine related SAE through to Day 365.
2. Secondary endpoints:
  - a. Detection of rVSV by PCR in blood, urine, and saliva in all subjects (D3, 7, 14, 28, 42 following each vaccination)
  - b. Detection of rVSV by PCR in through 42 days from skin vesicles, joint fluid, or skin biopsies if specimens are obtained
  - c. The occurrence of any SAE through to Day 365
  - d. Decrease in CD4 T cell-count (i.e.,  $CD4 < 200 \text{ mm}^3$ )
  - e. Increase in HIV viral load (i.e.,  $VL > 50 \text{ c/ml}$  over two consecutive measurements)

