### 8.2.5.2 Statistical Methods for Safety Analyses

Safety parameters will be compared between V920 and placebo control. Fisher's exact or Chi-square test will be used to compare the frequency of local and systemic reactions between treatment groups as specified in the SAP.

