### 8.2.5.3 Summaries of Baseline Characteristics, Demographics, and Other Analyses

Continuous variables, such as age and weight, will be characterized by descriptive statistics. Categorical variables, such as ethnicity, will be displayed by percentage frequencies.

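### Section 8 gives no analysis of the HIV-control endpoints (CD4 below 200; viral load above 50 c/ml twice running), and its stated laboratory summary, mean ± SD by arm, suits viral load poorly

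*Combined protocol and SAP*

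**What the plan says.** Secondary objective 3 (Section 3.2) is to "Evaluate the impact of V920 on HIV viral load, CD4 counts, and CD4/CD8 ratio". Section 4.2.3.2 gives it two secondary safety endpoints: 2.d, "Decrease in CD4 T cell-count" to below 200, and 2.e, viral load above 50 c/ml "over two consecutive measurements". Section 5.1.2 requires subjects to be on antiretroviral therapy with viral load below 40 c/ml. Both flow charts in Section 6.0 list viral load and CD4/CD8 among the laboratory procedures, at screening and at every visit to Day 365.

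Section 8 names neither endpoint. Section 8.2.3 has a subsection for immunogenicity endpoints only, and CD4 appears in Section 8 only as a cohort or subgroup factor. The text closest to these outcomes is:
- **8.2.5.2, laboratory paragraph:** mean values, with plus or minus "one standard deviation, will be summarized for each treatment group". Then: "Shift tables may also be generated if a significant frequency of abnormalities is noted". Then: "Extreme values will be discussed individually".
- **8.2.5.2, opening:** a general statement that the arms will be compared on safety. The only tests named, Fisher's exact or chi-square, are "used to compare the frequency of local and systemic reactions between treatment groups".
- **8.2.5.3:** "Categorical variables, such as ethnicity, will be displayed by percentage frequencies".

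**The concern.** For a live vaccine in people with suppressed HIV, the useful answer to objective 3 is how many subjects in each arm lost control and how uncertain the difference is. The protocol defines the right events but does not say how they will be analysed. The stated laboratory method, read onto viral load, answers a different question. Nearly all values should sit at the assay floor, so an arm mean reflects the size of a few rebounds more than their number. Endpoint 2.e also needs two successive values from the same subject, which an arm mean at a single visit does not contain. At stake is whether the report gives a comparative statement on HIV control that was fixed before unblinding, or a summary chosen afterwards.

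**Working it through.** The plan states no figure for viral load or CD4 outcomes, so there is nothing to reproduce. The arithmetic below is illustrative.

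**Inputs.** Arms of 200 and 50 with 10% dropout (Section 8.2.7): 200 × 0.9 = 180 V920 and 50 × 0.9 = 45 placebo. The dropout figure is the plan's own, stated for its immunogenicity power. Suppressed values are set to f = 40 c/ml, the entry limit. Rebound sizes r are assumed (1,000, 10,000 and 100,000 c/ml), as the documents give none.

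**1. Weight of one rebound in the arm total.** Share = r / [r + (n − 1)f].

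| n | r (c/ml) | Mean | SD | Share |
|---|---|---|---|---|
| 180 | 1,000 | 45.3 | 71.6 | 12% |
| 180 | 10,000 | 95.3 | 742 | 58% |
| 180 | 100,000 | 595.3 | 7,451 | 93% |
| 45 | 1,000 | 61.3 | 143 | 36% |
| 45 | 10,000 | 261.3 | 1,485 | 85% |
| 45 | 100,000 | 2,261 | 14,901 | 98% |

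One subject exceeds half the total when r > f(n − 1): 40 × 179 = 7,160 c/ml for V920 and 40 × 44 = 1,760 for placebo. With a floor of 20 these become 3,580 and 880.

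**2. The mean does not identify the count.** In 180 subjects, one rebound at 10,000 gives (179 × 40 + 10,000)/180 = 95.3. Ten rebounds at 1,036 give (170 × 40 + 10 × 1,036)/180 = 95.3. The rates are 1/180 = 0.6% and 10/180 = 5.6%. The SDs, 742 and 229, hint at the difference but do not give the number.

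**3. The mean can reverse the order of the arms.** Ten of 180 V920 subjects at 1,036 (5.6%) give 95.3. One of 45 placebo subjects at 10,000 (2.2%) gives 261.3. The arm with the higher rebound rate shows the lower mean.

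**4. A log scale or median does not replace the count.** Six of 200 at 1,000 (3%) give a geometric mean of 44.06. One of 50 at 10,000 (2%) gives 44.67. The order is again reversed, and both medians stay at 40.

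**5. What the count analysis can deliver at 180 versus 45.** Two-sided Fisher power is 2.4% for true rates of 5% versus 1%, and 54% for 10% versus 1%. If 9/180 versus 0/45 were observed, Fisher p = 0.21. The difference is 5.0 points, with an exact unconditional 95% CI (score-ordered, 0.25-point grid) of −3.25 to 9.25 points.

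**6. CD4 adjusted for Day 0.** The standard error relative to an unadjusted comparison of post-vaccination values is √(1 − r²), where r is now the correlation between Day 0 and later values. It is 0.87, 0.71 and 0.44 at r = 0.5, 0.7 and 0.9. These correlations are assumed.

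**The case against.** The laboratory paragraph never names viral load or CD4. Table 3 and the flow charts place them among laboratory tests, but they also list antibodies there, which have their own analysis, and Table 3 includes a pregnancy test, which has no mean. So applying mean ± SD to viral load is an inference. This stands. If the paragraph does not apply, however, objective 3 has no specific method in Section 8 at all.

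A reader might infer that the plan cannot show how many subjects lost HIV control. The documents do not support that. Endpoints 2.d and 2.e are binary, Section 8.2.5.2 promises a safety comparison, and Section 8.2.5.3 displays categorical variables as percentages, so percentages by arm are a fair reading. Still missing are a named analysis, a between-arm difference and an interval.

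A reader might also infer that a large rebound would go unseen. It probably would not, because individual discussion of extreme values is a firm commitment. That is a narrative with no threshold, count or comparison, though, and repeated values of 100 to 200 c/ml meet 2.e without necessarily being treated as extreme. Adverse-event reporting only partly fills the gap: non-serious events are collected to 42 days after each vaccination (Section 7.2), while viral load runs to Day 365.

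Finally, every rebound size is assumed, the equal-means example was constructed, and domination of the V920 mean is weak near 1,000 c/ml. All of that stands. The mismatch between an arm mean and a two-measurement event does not depend on those sizes.

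**Conclusion.** The point holds as an omission with a clear remedy. The protocol defines the right subject-level endpoints for objective 3, and Section 8 does not analyse them by name. The laboratory method it does state is unsuited to viral load in a population suppressed at entry. The domination figures rest on a floor of 40 c/ml, assumed rebound sizes and 10% dropout; in the V920 arm the effect is weak at 1,000 c/ml and strong from about 10,000. The Day 0 adjustment for CD4 is a gain in precision, not the repair of an error. No primary hypothesis, sample size or stopping rule depends on this, so it should be settled before database lock but does not threaten the trial's main conclusions.

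**What to change.** In Section 8.2.5.2, for secondary objective 3:

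1. Report n (%) of subjects meeting 2.e and 2.d in each arm, with the between-arm difference and an exact 95% CI. Replace raw mean ± SD for viral load with a log10 or median summary, labelled descriptive only.
2. Estimate the between-arm difference in CD4 count and CD4/CD8 ratio adjusted for the Day 0 value, which both flow charts already schedule.

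The cost is a few extra tables, with no new visits or samples. Section 8.0 allows changes to non-confirmatory analyses to go into a supplemental SAP before final database lock. The limitation is power: small differences in rebound rate will rarely reach significance, so the text should say that interpretation rests on the estimates and intervals and that a non-significant test is not reassurance.

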### 8.2.5.3 Summaries of Baseline Characteristics, Demographics, and Other Analyses

Continuous variables, such as age and weight, will be characterized by descriptive statistics. Categorical variables, such as ethnicity, will be displayed by percentage frequencies.

### 8.2.6 Multiplicity

Adjustment for multiplicity will not be performed.

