#### Primary Hypotheses:

- 1) The geometric mean titer (GMT) of GP-ELISA in V920 vaccinated HIV-infected adults and adolescents will be superior to the GMT of the GP-ELISA in placebo vaccinated HIV-infected adults at Day 28 in Cohorts 1-5 combined.
- 2) The geometric mean titer (GMT) of GP-ELISA in V920 vaccinated HIV-infected adults and adolescents will be superior to the GMT of the GP-ELISA in placebo vaccinated HIV-infected adults and adolescents Day 28 after the last dose of vaccine (equivalent to Day 84 from first dose) in Cohort 5

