### 8.2.2 Objectives/Hypotheses

(1) Objective: Evaluate the safety and tolerability of V920 in HIV-infected adults and adolescents.

(2) Objective: Evaluate the immunogenicity of V920 via ZEBOV-specific antibody responses induced by V920 at D28 in HIV-infected adults and adolescents.

Primary Hypotheses:

- 1) The geometric mean titer (GMT) of GP-ELISA in V920 vaccinated HIV-infected adults and adolescents will be superior to the GMT of the GP-ELISA in placebo vaccinated HIV-infected adults at Day 28 in Cohorts 1-5 combined.

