### 8.2.5 Statistical Methods

#### 8.2.5.1 Statistical Methods for Immunogenicity Analyses

Immunogenicity summaries will include: means and 95% CIs of the Geometric Mean Titers (GMT) and Geometric Mean Fold Increase from baseline (GMFI) of ZEBOV-specific antibody responses at baseline and Day 28, Day 84 (Cohort 5 only), Day 180, and Day 365.

Immunogenicity summaries will include: counts, percentages, and 95% CIs of subjects who achieve seroconversion (e.g. 4-fold increase) for ZEBOV-specific antibody responses at baseline and Day 28, Day 84 (Cohort 5 only), Day 180, and Day 365.

Immunogenicity summaries will include: counts, percentages, and 95% CIs of subjects who achieve seroprotection for ZEBOV-specific antibody responses at baseline and Day 28, Day 84 (Cohort 5 only), Day 180, and Day 365 based on correlate of protection thresholds, if found. Fisher's exact (primary) or Chi-square test (secondary if proportion size warrants) will be used to compare the frequency of ZEBOV-specific antibody responses and Student's t (primary) or Wilcoxon rank-sum test (secondary if not normally distributed) will be used to compare ZEBOV-specific GMT ZEBOV-specific antibody between treatment groups. All hypotheses will be evaluated using two-sided tests at  $\alpha = 0.05$ . Superiority of immune response will be defined as a statistically significant difference.

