### 8.2.7 Sample Size and Power Calculations

For immunogenicity assessment, there is 80% power to detect a Geometric Mean Ratio (GMR) of 1.6 (V920 GP-ELISA GMT of 58 EU/mL vs. Placebo GP-ELISA GMT of 36 EU/mL, the lower limit of quantification [LLOQ]) and 90% power to detect a GMR of 1.7 (V920 GP-ELISA GMT of 62 EU/mL) if comparing all five cohorts (N=200 V920 vs. N=50 Placebo) combined. This power analysis assumes a 10% dropout, a standard deviation of 1 on the log scale, and a 2-sided 5%.

There is 80% power to detect a GMR of 2.9 (V920 GP-ELISA GMT of 105 EU/mL) and 90% power to detect a GMR of 3.4 (V920 GP-ELISA GMT of 124 EU/mL) if comparing each cohort independently (N=40 V920 vs. N=10 Placebo). This power analysis assumes a 10% dropout, a standard deviation of 1 on the log scale, and a 2-sided 5%.

For safety assessment, there is 80% power to detect a 12% difference in event rates that occur with a frequency of 1% in the control group if comparing four cohorts (N=200 V920 vs. N=50 Placebo) combined and a 46% difference if comparing each cohort independently (N=40 V920 vs. N=10 Placebo).

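### The Cohort 5 Day 84 hypothesis is primary in two sections, overlaps a secondary objective in another and is missing from the SAP's primary list; and no success rule or testing order governs two unadjusted primary tests.

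*Combined protocol and SAP*

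**What the plan says.** **Hypotheses.** Section 3.1 gives two primary hypotheses, both that the GP-ELISA geometric mean titre (GMT) is higher on V920 than on placebo.
- H1 makes the comparison with "placebo vaccinated HIV-infected adults at Day 28 in Cohorts 1-5 combined".
- H2 makes it at "Day 28 after the last dose of vaccine (equivalent to Day 84 from first dose) in Cohort 5".

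**Where H2 stands elsewhere in the current text.**
- Section 4.2.3.1 lists the Cohort 5 response 28 days after the last dose as primary endpoint 1b.
- Section 3.2, secondary objective 5, is to "Evaluate the immunogenicity of two doses of V920 administered 56 days apart via ZEBOV-specific antibody responses induced by V920 at D28 post-dose 2".
- Section 8.2.2, under its own heading for primary hypotheses, lists one only: that the V920 GMT "will be superior to the GMT of the GP-ELISA in placebo vaccinated HIV-infected adults at Day 28 in Cohorts 1-5 combined".
- The summary in section 8.1 names the primary endpoints as safety and ZEBOV-specific antibody responses, which does not settle the matter.

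**Testing rules.** Section 8.2.5.1 says "All hypotheses will be evaluated using two-sided tests at" an alpha of 0.05, and then that "Superiority of immune response will be defined as a statistically significant difference". Section 8.2.6 consists of one sentence: "Adjustment for multiplicity will not be performed". No section gives an order of testing, says whether one or both hypotheses must be met, or states a family-wise error rate.

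**The concern.** There are two separate points.

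**Status of H2.** A reader of sections 3.1 and 4.2.3.1 would report H2 as a primary result. A reader of section 8.2.2 would not. If H1 and H2 came out differently, the two parts of the document would support different statements about whether the primary immunogenicity aim was met. The label also decides how a later change is handled: section 8.0 requires a protocol amendment for changes to primary or key secondary hypotheses or their methods, but only a supplemental SAP for exploratory or other non-confirmatory analyses.

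**Error rate.** If both hypotheses are primary and success on either is enough for a claim, two tests at full alpha give two chances of a false primary result. The plan neither limits this nor says that it is accepted for that reading.

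The second point does not follow from the first. It depends on a success rule that the plan does not state.

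**Working it through.** **Inputs from the documents.** Two-sided alpha 0.05 (8.2.5.1, 8.2.7); 4:1 allocation (5.3); standard deviation 1 on the log scale and 10% dropout (8.2.7); 200 vs 50 pooled and 40 vs 10 per cohort (8.2.7). After dropout these become 180 vs 45 and 36 vs 9. Placebo GMT is 36 EU/mL, the lower limit of quantification (8.2.7).

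**Input not in the documents.** The within-subject correlation *w* between Day 28 and Day 84 log titre. It is assumed, and varied over 0 to 1.

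**Step 1: the plan's own power figures.** With natural logs, the standard error of the difference in mean log titre is √(1/n_placebo + 1/n_V920).
- Pooled: √(1/45 + 1/180) = 0.1667.
- Single cohort: √(1/9 + 1/36) = 0.3727.

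Power comes from the noncentral t distribution with noncentrality ln(GMR)/SE, where GMR is the geometric mean ratio.

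| Comparison | GMR | Stated power | Recomputed | GMR giving exactly the stated power | Implied GMT (stated) |
|---|---|---|---|---|---|
| Pooled | 1.6 | 80% | 80.2% | 1.598 | 57.5 (58) |
| Pooled | 1.7 | 90% | 88.7% | 1.720 | 61.9 (62) |
| Single cohort | 2.9 | 80% | 79.8% | 2.91 | 104.8 (105) |
| Single cohort | 3.4 | 90% | 89.4% | 3.44 | 123.9 (124) |

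The stated figures reproduce, so the power rests on a full two-sided 0.05 for each comparison.

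**Step 2: error rate if both are primary and either suffices, with both nulls true.** For independent tests:
- Any rejection: 1 − 0.95² = 9.75%.
- A false claim in favour of V920 (0.025 per test): 1 − 0.975² = 4.94%.

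The tests are not independent, because Cohort 5 is in both. It supplies 50 of the 250 subjects, so the correlation between the test statistics is ρ = *w*√(50/250) = 0.447*w*. From the bivariate normal distribution, any rejection has probability 1 − P(|Z₁| < 1.96, |Z₂| < 1.96), and a false claim for V920 has probability 1 − P(Z₁ < 1.96, Z₂ < 1.96).

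| *w* (assumed) | ρ | Any rejection | False claim that V920 is superior |
|---|---|---|---|
| 0 | 0 | 9.75% | 4.94% |
| 0.5 | 0.224 | 9.62% | 4.82% |
| 0.7 | 0.313 | 9.49% | 4.75% |
| 0.9 | 0.402 | 9.32% | 4.66% |
| 1 | 0.447 | 9.21% | 4.61% |

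**Step 3: other readings.**
- Only H1 primary, as in 8.2.2: 5% two-sided, 2.5% in favour of V920.
- Both must be met: no more than 5% two-sided, so no adjustment is needed.

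**Step 4: what a fixed sequence would cost.** Under the order H1 then H2, H2 is lost whenever H1 fails. Power of H1 with 180 vs 45:
- At GMR 1.6: 80%.
- At GMR 2.0: noncentrality 0.693/0.1667 = 4.16, power 98.5%.
- At GMR 2.9: noncentrality 1.065/0.1667 = 6.39, power over 99.9%.

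So if the pooled Day 28 effect is near the 2.9 that gives a single cohort 80% power, placing H1 first takes practically nothing from H2.

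**The case against.** The strongest reply is that this is a Phase 2 trial which openly declares that it does not adjust. H1 asks about one dose across all cohorts and H2 about two doses in Cohort 5, and separate tests of separate prespecified questions can be defended. This has force: unadjusted testing is not wrong in itself. It would be enough if the plan said that the two claims are separate and listed both in section 8.2.2. It does neither.

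The practical risk is also small. Inflation needs both nulls to be true; if H1 is truly met, the only possible false primary claim is H2, at its own 5%. The comparator is saline, and section 4.1.3 reports that all Phase 1 subjects seroconverted by 28 days, although that was not an HIV-infected population. This stands, and it limits how serious the point is.

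Secondary objective 5 is broad and carries no hypothesis. It could cover fold increase, seroconversion and neutralization, so it overlaps H2 and does not duplicate it. This also stands.

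Four stronger readings are tempting but not supported:
- **That the false-claim rate is about 9.5%.** That value needs a correlation near 0.7, which the documents do not give, and it counts results in favour of placebo. Section 8.2.5.1 defines superiority without direction, but both hypotheses supply one.
- **That the trial departs from a promised 5% family-wise rate.** The 5% in the plan is a per-test level.
- **That the sponsor may freely choose the status of H2 after seeing the results.** Section 8.0 requires an amendment for changes to primary hypotheses before database lock. The weakness is narrower: the existing text already supports two readings.
- **That there are four primary tests,** because section 4.2.3.1 names both ELISA and neutralization for each endpoint. The stated hypotheses cover GP-ELISA only.

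**Conclusion.** The first point holds without assumptions: sections 3.1 and 4.2.3.1 make the Cohort 5 Day 84 comparison primary, section 8.2.2 omits it, and section 3.2 overlaps it.

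The second point holds conditionally. If both hypotheses are primary and either alone supports a claim, the chance of any rejection under the global null is 9.2% to 9.75%, and the chance of falsely claiming V920 superior is 4.6% to 4.9% against 2.5% for a single test. The ranges cover every within-subject correlation from 0 to 1, so they do not rest on a chosen value. They do rest on the planned cohort sizes and on approximate normality of the test statistics. If only H1 is primary, or both must be met, nothing is inflated. The defect is that the plan does not say which rule applies.

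This should be corrected before database lock. It does not threaten the trial, since failure of H1 looks unlikely.

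**What to change.** 1. Add H2 to the primary hypotheses in section 8.2.2, so that it agrees with sections 3.1 and 4.2.3.1. Reword secondary objective 5 in section 3.2 to the two-dose questions that H2 does not cover.
2. In section 8.2.6, replace the sentence, for the primary hypotheses, with a fixed sequence: test H1 at two-sided 0.05; test H2 at two-sided 0.05 only if H1 is significant in favour of V920.
3. State that other immunogenicity tests remain unadjusted and lie outside the primary claim.

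The sequence holds the two-sided family-wise error at 5% (2.5% in favour of V920) without splitting alpha or adding subjects. The alternative is to test each hypothesis at 0.025, which gives 1 − 0.975² = 4.94% if independent and at most 5% otherwise, but lowers the power of the small Cohort 5 comparison.

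**Cost.** More than a wording change to the SAP: section 8.0 calls for a protocol amendment before database lock, and the statement that closes the Amendment History requires local ethics board approval. The statistical price is that H2 cannot be claimed if H1 fails: about a 20% chance at a pooled GMR of 1.6, 1.5% at 2.0 and below 0.1% at 2.9.
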